8.3. PROCEDURES FOR AE REPORTING BY THE INVESTIGATOR

AEs will be monitored throughout the study. AE reporting will start with the first dose of investigational product. AEs will be reported through the conclusion of Visit 6. AEs will be recorded on the CRF with the date and time of onset, date and time of resolution, severity, seriousness, causality (relationship to use of investigational product), treatment required, and the outcome. To elicit AEs, simple questions with minimal suggestions or implications should be used as the initial questions at all evaluation points during the trial. For example:

- How has your child felt since their last visit?
- Has your child had any health problems since your last visit?

The severity of each AE should be categorized as mild, moderate, or severe.

The causality of use of investigational product in relation to the AE will be assessed by the Principal Investigator after careful medical consideration and categorized as unrelated, unlikely, possible, probable, or definite.

If an AE occurs, the Investigator will institute support and/or treat as deemed appropriate. If an AE is unresolved at the time of the last study visit, an effort will be made to follow up until the AE is resolved or stabilized, the subject is lost to follow-up, or there is some other resolution of the event. The Investigator should make every attempt to follow SAEs to resolution.

8.4. SERIOUS ADVERSE EVENT REPORTING BY THE INVESTIGATOR**Serious Adverse Event Reporting**

It is the responsibility of the Investigators or their designees to report any event of this nature to the sponsor or a designee within 24 hours of the event being brought to the Investigators' or their staffs' attention. In the event of an SAE, the Investigator or site designee must fax the Kala Clinical Study Serious Adverse Event Form within 24 hours of becoming aware of the event to Drug Safety Navigator at [contact]. It is also the responsibility of the Investigator to report all SAEs reported at their site to their Institutional Review Board (IRB), as required. The Investigator should make every attempt to follow all SAEs to resolution.

The following information should be provided when an SAE is reported to the sponsor or designee:

1. Protocol Number
1. Site Number
2. Subject Number
3. Subject Demographic information, including:
 - Date of Birth
 - Sex
 - Race
4. Investigational product start date
5. Date of last dose of investigational product
6. Date investigational product reinitiated (if investigational product interrupted)
7. SAE information, including:
 - SAE term (diagnosis only; if known or serious signs/symptoms)
 - Description of SAE/narrative
 - Date/time of onset
 - Severity
 - Outcome
 - Date/time of resolution or death (if duration < 24 hours)
 - Relationship to investigational product
 - Action taken with investigational product
8. Criteria for classifying the event as serious, including whether the SAE:
 - Resulted in death.
 - Was life-threatening.
 - Required inpatient hospitalization.
 - Prolonged inpatient hospitalization.

- Resulted in a persistent or significant incapacity or substantial disruption of the ability to conduct normal life functions.
 - Was a congenital anomaly/birth defect.
 - Important medical events that may not result in death, were not life-threatening, or did not require hospitalization may be considered serious when, based upon appropriate medical judgment, they may jeopardize the patient or subject and may require medical or surgical intervention to prevent one of the outcomes listed in this definition. Examples of such medical events include allergic bronchospasm requiring intensive treatment in an emergency room or at home, blood dyscrasias or convulsions that do not result in inpatient hospitalization, or the development of drug dependency or drug abuse.
9. Concomitant medications
 10. Relevant history
 11. Possible causes of SAE other than investigational product
 12. Copy of AE page from the eCRF

NOTE: If an SAE occurs in any study involving KPI-121 1% ophthalmic suspension that is unexpected and is determined to be related or possibly related to investigational product, all sites will be notified by the sponsor and each site should report it to its IRB.

9. STATISTICS**9.1. STATISTICAL METHODS**

Continuous measures (e.g., age) will be summarized descriptively by the mean, standard deviation, median, minimum and maximum values. Categorical measures will be summarized by the number and percent of subjects.

9.1.1. Subject Disposition, Demographic and Background Characteristics

Subject disposition, demographic characteristics, and background variables will be summarized by study group.

9.1.2. Evaluation of Efficacy

The efficacy and safety evaluations will be based on a single study eye, defined as the surgery eye, for each subject.

The primary analysis population will be the Intent-to-Treat (ITT) population, defined as all subjects randomized and with at least one post-baseline assessment. A subset of efficacy analyses will be repeated using data from those subjects who were randomized, completed 15 days \pm 2 days of investigational product use, had complete data at Visit 4 (Day 15 \pm 2 days), and did not have significant protocol deviations, the Per Protocol (PP) population. Rescued subjects will be included in the PP population if they did not have significant protocol deviations, however, these subjects will be considered treatment failures.

No inferential statistical analyses are planned. Data will be summarized using descriptive statistics only. Assessment of efficacy will be based primarily on the number and percentage of subjects in each treatment group with an anterior chamber cell grade of 0 at Visit 4 (Day 15 \pm 2 days) with no need for rescue medication through Visit 4 and, secondarily, on the Modified Global Overall Assessment of Postoperative Inflammation score of 0 at Visit 4 (Day 15 \pm 2 days) without receiving rescue medication prior to Visit 4.

The individual components of the Global Assessment score will also be evaluated (i.e., number and percentage of subjects in each treatment group in each score category at each visit).

The following scoring scale for anterior chamber cells will be used:

0 = No cells seen

1 = 1 - 5 cells

2 = 6 - 15 cells

3 = 16 - 30 cells

4 = greater than 30 cells

The following signs and symptoms scoring scales for inflammation will be used:

SIGNS	Grade 0	Grade 1	Grade 2	Grade 3	Grade 4
Anterior Chamber Cells	0 cells	1 - 5 cells	6 - 15 cells	16 - 30 cells	> 30 cells
Anterior Chamber Flare	Absent	Mild (trace to clearly noticeable, visible)	Moderate (without plastic aqueous humor)	Marked (with plastic aqueous humor)	Severe (with fibrin deposits and/or clots)
Corneal Clarity	Absent	Mild	Moderate	Severe	
Conjunctival Injection	Absent	Mild	Moderate	Severe	
Chemosis	Absent	Mild	Moderate	Severe	
Hypopyon	Absent	Mild	Moderate	Severe	
Vitritis	Absent	Mild	Moderate	Severe	
Wound Integrity	Absent	Mild	Moderate	Severe	
SYMPTOMS	Grade 0	Grade 1	Grade 2	Grade 3	
Photophobia	Absent	Mild	Moderate	Severe	
Lacrimation	Absent	Mild	Moderate	Severe	

Modified Global Overall Assessment of Postoperative Inflammation

Based on the signs and symptoms scoring above the following overall categorization of inflammation will be assessed:

- 0 Clear
- 1 Improving satisfactorily
- 2 Not improving or worsening; allow rescue therapy

9.1.3. Analysis of Safety

Analysis of safety data will be presented for all subjects in the Safety population (i.e., all subjects receiving randomized investigational product). AEs will be coded using Medical Dictionary for Regulatory Activities (MedDRA, version 21.0) and categorized by system organ class using preferred terms. AEs will be tabulated by study group with respect to their intensity and relationship to the investigational product. Ophthalmoscopy findings will be summarized descriptively. IOP measurements, Visual Acuity and Dilated Ophthalmoscopy assessments will be summarized as safety outcomes.

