	
The primary analysis population will be the Intent-to-Treat (ITT) population, defined as all subjects randomized and with at least one post-baseline assessment. A subset of efficacy analyses, the Per Protocol (PP) population, will be repeated using data from those subjects who were randomized, completed 15 days \pm 2 days of investigational product use, had complete data at Visit 4 (Day 15 \pm 2 days), and did not have significant protocol deviations. Rescued subjects will be included in the PP population if they did not have significant protocol deviations: however, these subjects will be considered treatment failures.
 
No inferential statistical analyses are planned. Data will be summarized using descriptive statistics only. Assessment of efficacy will be based primarily on the number and percentage of subjects in each treatment group with an anterior chamber cell grade of 0 at Visit 4 (Day 15 \pm 2 days) with no need for rescue medication through Visit 4 and, secondarily, on the Modified Global Overall Assessment of Postoperative Inflammation score of 0 at Visit 4 (Day 15 \pm 2 days) without receiving rescue medication prior to Visit 4.
 
The individual components of the Global Assessment score will also be evaluated (i.e., number and percentage of subjects in each treatment group in each score category at each visit).

Safety Evaluations:	
Assessment of AEs
 
Change from baseline to each post-surgery visit in ocular signs:
 
 • Visual Acuity • IOP Measurement • Dilated Ophthalmoscopy (at Visits 1 and 5 only) 
Assessment of safety will be based on the assessment of AEs. To allow for at least a 95% chance of detecting an AE with a 10% incidence rate, a minimum sample size of 30 subjects per group (KPI-121 1% or prednisolone acetate 1%) is required.

Eligibility Criteria:	
Inclusion Criteria:
 
At Visit 1, individuals of either gender and any race will be eligible for study participation if they:

1. Have informed consent and Health Insurance Portability and Accountability Act (HIPAA) authorization provided by parent or guardian prior to any study-related procedures.
2. Are 0-3 years of age (have not had their 4th birthday) as of the date of surgery.
3. Are candidates for routine, uncomplicated, cataract surgery
 - a. With or without capsulotomy and vitrectomy
 - b. With or without posterior chamber intraocular lens (IOL) implantation

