3.3. SAFETY ENDPOINTS

Safety evaluations will include:

- Assessment of AEs
- Visual Acuity
- IOP Measurement
- Dilated Ophthalmoscopy (assessed at visits 1 and 5 only)

Ocular assessments will be summarized at each post-surgery and compared between the KPI-121 1% dosed BID and the prednisolone acetate 1% dosed QID treatment arms.

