5.1.9. Unscheduled Visit

Any visits or procedures performed beyond those specified within the protocol must be documented in the Unscheduled Visit pages of the eCRF. Unscheduled visits may include but are not limited to reporting adverse events (AEs), changes in concomitant medications, or ophthalmic assessments as deemed appropriate by an appropriately qualified physician. If the subject is discontinuing study participation at the unscheduled visit, the Early Termination eCRFs should be completed rather than the Unscheduled Visit eCRFs.

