6.2. CONCOMITANT MEDICATIONS

With the exception of peri-operative standard of care medications, all medication that the subject has taken 30 days prior to Visit 1 and through Visit 6 or discontinuation from the study will be recorded in the subject's chart/source documents and the eCRF. The name of the drug, dose, route of administration, duration of treatment (including start and stop dates), frequency, indication, and whether or not the medication was taken due to an AE will be recorded for each medication.

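### By-visit IOP tables mix pressures read after pressure-lowering treatment with the rest and make no provision for unscheduled readings, so they can understate a difference between arms

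*Combined protocol and SAP*

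**What the plan says.** IOP is a safety endpoint (sections 3.3 and 8.1), measured at every clinic visit where obtainable (Appendices 1 and 4). Section 9.1.3 says that "IOP measurements, Visual Acuity and Dilated Ophthalmoscopy assessments will be summarized as safety outcomes". That sentence does not mention visits. The visit-by-visit form comes from the synopsis (Safety Evaluations), which lists IOP under "Change from baseline to each post-surgery visit in ocular signs", and from section 3.3: "Ocular assessments will be summarized at each post-surgery and compared" between the two arms. Under section 9.1, continuous measures are "summarized descriptively by the mean, standard deviation, median, minimum and maximum values". The Safety population holds every child who received study drug, so a child treated for pressure stays in the table.

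On treatment, section 8.3 says: "If an AE occurs, the Investigator will institute support and/or treat as deemed appropriate". Section 6.2.2 does not permit topical medication in the study eye during the study, and its exceptions do not name pressure-lowering drops. For concomitant medicines, section 6.2 collects start and stop dates and indication, and "whether or not the medication was taken due to an AE will be recorded for each medication". Section 5.1.9 says that unscheduled visits may cover "changes in concomitant medications, or ophthalmic assessments as deemed appropriate" and gives them their own eCRF pages.

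The plan does not say how a pressure read after pressure-lowering treatment is handled, or whether an unscheduled pressure enters any table. It has no count of children above a pressure level. The 21 mmHg figure in sections 4.2 and 4.3 serves eligibility only. The one missing-data rule (section 9.4) concerns the Day 15 efficacy time point.

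**The concern.** Every child must have IOP of 21 mmHg or less to be randomized. A child whose pressure then rises, is treated and falls back therefore contributes an ordinary value at the next visit, with nothing to mark it as a treated value. If the high reading was taken at an unscheduled visit, no by-visit table need show it. Clinic visits fall on Days 8, 15, 29 and 36, with only a phone call between Days 15 and 29, so discovery between visits is plausible.

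The trial compares two topical steroids, and the protocol excludes children with a history of steroid-induced pressure rise, so it recognises the risk itself. The analysis is descriptive only (section 9.3), so a reader will judge pressure safety from these tables. Similar mean pressures in the two arms could partly reflect the pressure-lowering medicine rather than similar effects of the two steroids.

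**Working it through.** **The plan's own figure.** Section 9.2 gives 30 per group for at least a 95% chance of seeing an AE with 10% incidence. 1 − 0.9^30 = 0.958, so the figure reproduces (29 gives 0.953 and 28 gives 0.948). It is not in dispute; it supplies the 30 used below.

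**Assumptions.** The documents give no rise rate, rise size, IOP standard deviation or response to treatment. All four are assumed here.

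**One later visit.** If k treated children in an arm of 30 would each have been higher by a fixed rise, and treatment returns them fully to baseline, the arm mean is lower by k × rise / 30.
- One child, rise of 8 to 16 mmHg: 8/30 = 0.27 to 16/30 = 0.53 mmHg.
- Four children in one arm and one in the other, 12 mmHg: 4 × 12/30 − 1 × 12/30 = 1.6 − 0.4 = 1.2 mmHg masked.
- The same split at 8 or 16 mmHg: 3 × 8/30 = 0.8 or 3 × 16/30 = 1.6 mmHg.

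For a given split and rise these are upper limits, because every rise is taken as treated and fully reversed before that visit.

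**All visits.** Suppose a 12 mmHg rise, onset spread evenly over Visits 3 to 5, and treatment restoring pressure by the next visit. Then one third of the rises show at each of those visits. For 6 v 2 children: untreated at Visit 5, 12 × (6 − 2)/30 = 1.60; as observed with treatment, 12 × (2 − 0.67)/30 = 0.53. If half the rises are found only at unscheduled visits, the observed figure halves.

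| Children with a rise (of 30 v 30) | Any-time rate | Mean difference at Visit 5, untreated | At each of Visits 3–5, treated | Same, half found unscheduled |
|---|---|---|---|---|
| 3 v 1 | 10% v 3.3% | 0.80 | 0.27 | 0.13 |
| 6 v 2 | 20% v 6.7% | 1.60 | 0.53 | 0.27 |
| 9 v 3 | 30% v 10% | 2.40 | 0.80 | 0.40 |

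If every rise is found at an unscheduled visit, the treated difference is 0 at all scheduled visits. If none is, it is 0 only at Visit 6. A simulation (4,000 runs, assumed mean 13 and SD 3 mmHg) agrees within simulation error: for 6 v 2 it gives 0.55, 0.52 and 0.54 at Visits 3, 4 and 5 and 0.00 at Visit 6, against 1.58 untreated at Visit 5. With that SD, the standard error of a mean difference is 3 × √(2/30) = 0.77 mmHg.

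**Direction.** The tables understate a difference when rises are treated at similar rates in both arms. With unequal treatment they can do the opposite. Take 4 rises of 12 mmHg in each arm, with 1 treated in one arm and 4 in the other: the untreated difference is 0, but the table shows 3 × 12/30 = 1.2 mmHg.

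**A measure that does not dilute.** A count of children ever raised or ever treated keeps the any-time rates in the second column, whenever treatment began and at whichever type of visit the rise was found.

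**The case against.** The strongest reply is that IOP tables are not the main safeguard. The synopsis and section 9.2 rest safety on AEs. Treatment under section 8.3 follows an AE, so a rise treated by that route is already an AE, recorded with onset, resolution and treatment and tabulated by arm wherever it was found. Four treated rises against one would then show as 4 against 1. This stands, and it rules out an inference that a reader might draw: that treated rises vanish from the safety report. What remains is that no passage defines when a pressure rise is an AE, so capture depends on the investigator, and the AE table does not correct the IOP table.

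Two other stronger readings also fail. A reader might infer that the distortion always favours the arm with more rises. The documents do not support this: treatment is discretionary, the number treated, timing and response may differ by arm, and study drug may be stopped (section 5.2), which may itself lower pressure. A reader might also infer that the difference disappears throughout. A rise measured at a scheduled visit enters that visit's mean and maximum, so the signal there is diluted, not lost.

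Finally, replacing treated values with the last pre-treatment pressure might seem the natural remedy. That value will often be near a peak. Carrying it forward, even to Visit 6 after study drug has ended, would make short rises look sustained.

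**Conclusion.** The point holds in a limited form. As written, the by-visit and change-from-baseline IOP tables can understate a difference between arms at visits after treatment starts, given similar treatment rates, and can miss rises found only at unscheduled visits. With 4 v 1 treated children and a 12 mmHg rise, at most 1.2 mmHg is masked at a later visit. In the spread-out illustration, 1.60 untreated becomes 0.53 observed at Visit 5 for 6 v 2 children. Both results rest on assumed rates, rise sizes and full response to treatment; they show how the distortion works and do not predict its size. The primary efficacy result is untouched. This is a cheap improvement to a named safety comparison rather than a flaw in the design.

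**What to change.** In section 9.1.3:
- Keep the as-observed by-visit and change-from-baseline tables as the main presentation.
- Flag each study-eye pressure taken after the start of a recorded pressure-lowering medicine.
- Beside those tables, give the number and percentage of children per arm who, at any post-baseline time, scheduled or unscheduled, had study-eye IOP above a pre-stated cut-off or started pressure-lowering treatment. The protocol's own 21 mmHg could serve, for analysis only and not as a trigger for care.
- Add peak change in study-eye IOP from baseline, including unscheduled readings. State which visit is the baseline, since the plan does not. A peak tends to grow with the number of readings, so show readings per child by arm.
- Do not make a carried-forward pre-treatment pressure the main table.

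Sections 6.2.2 and 8.3 should also be reconciled on how pressure-lowering treatment of the study eye is recorded and analysed.

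The cost is one extra table and one derivation, with no new visit or procedure. Medication dates, indication, AE link and unscheduled assessments are already in the eCRF. There are two limits. Routine peri-operative medicines that are not continued after surgery stay in source documents (sections 5.1.2 and 6.2.1). Section 6.2 covers medicines, so a procedure would have to be found in the AE treatment field or the unscheduled-visit pages. The wording should be fixed before unmasking.

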4.2. SUBJECT EXCLUSION CRITERIA

In order for subjects to be eligible at Visit 1 they may not:

1. Have a post-traumatic cataract.
2. Have suspected permanent low vision or blindness in the fellow non-study eye.
3. Have active uveitis in either eye.
4. Have an ocular neoplasm in either eye.
5. Have the presence of any active or suspected viral, bacterial, or fungal disease in either eye.
6. Have a history of glaucoma, ocular hypertension, steroid-induced IOP rise or have an IOP >21 mmHg in either eye at the screening or randomization visit(s).
7. Require the use of any topical ophthalmic medication in the study eye within 2 days prior to surgery and for the duration of the study, except for

- drops that are needed to examine the eye or to prepare for and undergo surgery as well as post-operative antibiotic drops. **NOTE:** Besifloxacin Ophthalmic Suspension is not permitted within 2 days prior to surgery or for the duration of the study.
8. Require the use of systemic or ocular non-steroidal anti-inflammatory drugs within 2 days prior to surgery and for the duration of the study.
 9. Require treatment with systemic, inhaled or ocular corticosteroids within 14 days prior to surgery and for the duration of the study with the exception of intraoperative ocular corticosteroids.
 10. Require a change in use of nutraceuticals or multivitamins within 2 days prior to surgery and for the duration of the study.
 11. Have known hypersensitivity or contraindication to the investigational product(s) or their components.
 12. Have a diagnosis of:
 - a. Severe/serious ocular condition that in the judgment of the Investigator could confound study assessments or limit compliance.
 - b. Severe/serious systemic disease or uncontrolled medical condition that in the judgment of the Investigator could confound study assessments or limit compliance.
 13. Have been exposed to an investigational product within 30 days prior to surgery.

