9.2. SAMPLE SIZE ESTIMATION

Assessment of safety will be based on the assessment of AEs. To allow for at least a 95% chance of detecting an AE with a 10% incidence rate, a minimum sample size of 30 subjects per group (KPI-121 1% or prednisolone acetate 1%) is required. All statistical analyses will be performed using Statistical Analysis System (SAS) software.

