APPENDIX 4: IOP MEASUREMENT

IOP measurements will be performed utilizing an Icare rebound tonometer, or similar tonometer according to the Investigator's standard procedure. All pressures will be recorded in mmHg.

IOP will be assessed at all study visits (when obtainable, except at Visit 2 when this assessment is required). If unable to obtain a valid measurement by tonometer at Visit 2, assessment by other means, as determined by the investigator, will be accepted.

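### The planned IOP summaries cannot show how many children in each arm had a pressure rise; add a per-arm count above 21 mmHg

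*Combined protocol and SAP*

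**What the plan says.** Section 3.3 names four safety endpoints: AEs, visual acuity, IOP and dilated ophthalmoscopy. It says the ocular assessments will be summarized after surgery and compared between the arms.

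For the analysis itself, Section 9.1.3 states that "IOP measurements, Visual Acuity and Dilated Ophthalmoscopy assessments will be summarized as safety outcomes". It names no statistic. The only stated method for a measurement in mmHg is the general rule in Section 9.1: "Continuous measures (e.g., age) will be summarized descriptively by the mean, standard deviation, median, minimum and maximum values". The synopsis, under Safety Evaluations, lists IOP under the line "Change from baseline to each post-surgery visit in ocular signs".

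The data are collected. Appendix 4 says "IOP will be assessed at all study visits (when obtainable, except at Visit 2 when this assessment is required", with values recorded in mmHg.

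The protocol also has an IOP limit of its own. Section 4.2 excludes children who "Have a history of glaucoma, ocular hypertension, steroid-induced IOP rise or have an IOP >21 mmHg in either eye", and Section 4.3 repeats the 21 mmHg limit for both eyes at randomization.

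The other route by which a rise could be reported is the AE table in Section 9.1.3: "AEs will be tabulated by study group with respect to their intensity and relationship to the investigational product". No section gives an IOP value that makes a rise an AE. None plans a count of children above an IOP level, a count with a given rise, or each child's highest value.

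**The concern.** Safety stands beside efficacy in the objective (Section 2.1), and the sample size is justified on the chance of seeing an event: "To allow for at least a 95% chance of detecting an AE with a 10% incidence rate". That is a statement about affected children, whereas the IOP summaries describe the distribution of readings at each visit. If a few children in one arm have a large rise, the mean moves little. The SD and maximum may hint at it, but the reader cannot recover the number of children. A maximum at each of Visits 3 to 6 could be one child four times or four different children.

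The efficacy section handles this better: Section 9.1.2 asks for the number and percentage in each score category at each visit. IOP gets nothing comparable, although the readings would support it.

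**Working it through.** **The plan's own figure.** Inputs from Section 9.2: 30 per group, 10% incidence, target 95%. P(at least one event) = 1 − (1 − p)^n.
- n = 28: 94.8%
- n = 29: 95.3%
- n = 30: 95.8%

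The exact minimum is 29, so the stated 30 is sound.

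**Do the five planned statistics fix the number of children above 21 mmHg?** A random search over constructed data sets of 30 readings found sets with 2, 3, 4, 5 and 6 values above 21 mmHg that agree on all five statistics. The two extremes are (value × frequency):
- Set A: 10×5, 12×7, 14×4, 16×4, 18×3, 20×5, 30×2. Two values exceed 21 (2/30 = 7%).
- Set B: 10×4, 12×7, 14×8, 16×3, 18×1, 20×1, 22×4, 28×1, 30×1. Six values exceed 21 (6/30 = 20%).

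Both sum to 468, so the mean is 468/30 = 15.6. Both have a sum of squares of 8088, so SD = √[(8088 − 30 × 15.6²)/29] = √(787.2/29) = 5.21. Both have median 14, minimum 10 and maximum 30. A table built to Section 9.1 would print the same row for each. The data are invented to test the summary; they do not predict this trial.

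**What a rise in a few children does to the summary.** Assumptions, none from the documents: 3 of 30 children in one arm rise by 12 mmHg, the rest do not change on average, and the SD of change is otherwise 3 to 5 mmHg.
- Mean shift = 3 × 12/30 = 1.2 mmHg (1.0 to 1.5 if the rise is 10 to 15 mmHg).
- SD in that arm = √(s² + 0.1 × 0.9 × 12²) = √(s² + 12.96), which gives 4.7, 5.4 and 6.2 for s = 3, 4 and 5.
- SE of the difference in means = √[(s² + 12.96 + s²)/30], which gives 1.0, 1.2 and 1.4 mmHg.

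The mean shift is about the size of its standard error. The wider SD and a high maximum would be visible, but not the number 3.

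**What a count would show.** Exact (Clopper-Pearson) 95% intervals at n = 30:
- 0/30: 0% to 11.6%
- 3/30: 2.1% to 26.5%
- 6/30: 7.7% to 38.6%

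The chance of seeing at least one such child is 45.5%, 78.5%, 95.8% and 99.9% for assumed true rates of 2%, 5%, 10% and 20%.

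**Can it be built from the data?** Yes. Entry requires 21 mmHg or less in both eyes at Visit 2, so a later study-eye reading above 21 is new. Readings are planned at Visits 3 to 6, when obtainable.

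**The case against.** **The planned statistics do show something.** Applied to change from baseline, the maximum gives the largest individual rise per arm at every visit, and the SD widens when a few children respond. This stands. The gap is the number of children and whether a rise persisted, so to say that the plan conceals all rises would go too far.

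**AEs are tabulated by arm.** The exemption for expected postoperative inflammation (Sections 5.1.3 and 8.2) does not cover IOP, so a rise judged untoward would be counted. A reader might infer that no rise will ever be counted; the documents do not support that. But with no IOP level set, the decision rests with about 20 sites averaging 60/20 = 3 children each. The suggested opening AE questions ask parents how the child felt (Section 8.3), which may not bring out a rise without symptoms.

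**A count is also imprecise.** The intervals for 3/30 and 0/30 overlap, and a two-sided Fisher test gives p of about 0.24. True, but the plan is descriptive (Section 9.3). The case for a count is that it reports the quantity of interest, and it offers no gain in power.

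**21 mmHg is an entry limit and not a stated safety threshold.** Agreed. It is used here only as an analysis category and carries no implication for how a child is managed.

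**The count needs rules the plan lacks.** Also agreed. The baseline visit is not named, denominators will vary, a Visit 2 assessment may lack a valid tonometer value (Appendix 4), and rescued children stop product but stay in the study (Section 5.4). The fix has to cover these.

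**Conclusion.** The point holds as a gap in safety reporting that should be closed. On the plan as written, the number of children per arm with raised IOP cannot be recovered from the IOP tables: identical summaries are compatible with 2 to 6 of 30 above 21 mmHg. AE tabulation fills the gap only in part and without a common criterion. Design, sample size and data collection are not affected.

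Two things limit the conclusion. First, applying the Section 9.1 statistics to IOP is an inference, because Section 9.1.3 names none; Section 9.5 refers to a statistical analysis plan, and nothing beyond this text was available. Second, the size of rise and the SDs in the illustration are assumptions. The constructed data sets need no such assumption, because they only show that the summary does not determine the count.

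A reader might go further and infer that IOP rise is the main expected harm of both steroids, or that it affects a minority of children. The documents say neither. They list IOP as one of four safety endpoints and mention steroid-induced rise only as an exclusion.

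**What to change.** Add to Section 9.1.3, by arm, for the study eye in the Safety population:

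- The number and percent with IOP above 21 mmHg at each post-dose visit and at any post-dose visit. State that 21 mmHg is the protocol's entry limit, used only as an analysis category.
- As denominator, the children with an obtainable IOP at that visit (for the any-visit count, at least one obtainable post-dose IOP), printed in the table.
- Exact 95% confidence intervals, labelled as descriptive precision.
- A subject listing of these children with all their readings, so that persistence can be seen.
- On-product visits shown separately from visits after a switch to rescue or after product ends (Visit 6).

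A count with a prespecified rise from baseline may be added if the sponsor sets the cut-off and names the baseline visit. Children whose Visit 2 IOP has no numeric tonometer value would be left out of that count and their number stated.

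The cost is one extra table, one listing and a little specification work before unmasking. No new data, visits, subjects or hypothesis tests are needed.
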